7. ASSOCIATED ACTS/TREATMENTS/PROCEDURES

7.1. Authorized associated acts/treatments/procedures

NA

7.2. Associated acts/treatments/procedures prohibited

NA

[figure not shown]
7.3. CARE-RESEARCH DISTINCTION

MANAGEMENT COMPARISON TABLE

| Procedures and treatments | Care-related procedures | Research-related acts |
|---------------------------|-------------------------|-----------------------|
| Hospitalization | X | |
| FES-I questionnaire | | X |
| Hip goniometry | | X |
| Schober index | | X |

8. RESEARCH PROCESS

The diagram below shows the research process.

8.1. Research schedule

- Start of inclusion: September 2021
- Length of inclusion period: 6 months
- Duration of each patient's participation: 30 minutes
- Total duration of research: 6 months, can be stopped early as soon as the required number of patients of patients required

8.2. Summary table of patient follow-up

There is no patient follow-up for this study.

Summary table of research phases

| | Inclusion T 0 |
|----------------------|------------------|
| Information | ✓ |
| No opposition | ✓ |
| Questionnaire | ✓ |
| Clinical examination | ✓ |

8.3. INFORMATION FOR PERSONS CONCERNED

In accordance with article L1122-1 of the French Public Health Code, prior to the performance of research involving the human person, information is provided to the person participating in the research by the investigator or by a physician representing the investigator. When the investigator is a qualified person, this information is provided by that person or by another qualified person representing him or her.

In accordance with article L1122-1-1 of the French Public Health Code, no research mentioned in 3° of the same article L. 1121-1 may be carried out on a person if that person has objected to it.

Before any research-related procedures or examinations are carried out, the investigator must inform the patient.

Patient information will be provided during the consultation. Patients will be informed directly by the investigator, and will have the opportunity to ask questions and object to their participation in the study.

8.4. Visit

The study will take place during the patient's consultation, at which time the study will be proposed to the patient. During the consultation and before any research-related examination, the investigator proposes that the patient to take part in this research and informs him/her of the following in particular:

- the objective, methodology and duration of the study
- Expected benefits
- The computerized processing of data concerning the patient that will be collected in the course of the research, and the patient's rights of access, opposition and rectification.

A copy of the information document is given to the patient prior to participation in the research.

During this visit, the investigator also checks the patient's eligibility criteria. If the patient agrees to participate, he or she gives oral consent during the consultation.

This information is recorded in the patient's medical record.

The non-opposition of the patient will be recorded in the patient's medical file by the investigator or qualified qualified person.

Any amendment that modifies patient management or the benefits, risks and constraints of the research will be the subject of a new information document. The procedure for informing the persons concerned is the same as that described above.

8.5. Randomization

NA

8.6. End-of-research visit

There is only one end-of-study visit.

8.7. Special monitoring procedures

NA

8.8. Research termination rules

For this study, the stopping rules will be :

- Inability or refusal of the included patient to perform one of the measurements (hip goniometry or Schober index measurement).
- Incomplete FES-I questionnaire
- Occurrence of a non-inclusion criterion

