1 / evaluation of the fear of falling using an FES-I questionnaire, distribution of subjects according to the score into 3 groups (16-19: little concerned by the fear of falling, 20-27 moderately concerned, 28-64 very concerned by fear of falling)

2 / evaluation of lumbar articular mobility by the schober index, coxofemoral by hip goniometry in flexion and extension (no evaluation of other amplitudes because lack of abduction / abduction / external and internal rotation of the hip remain functional in walking and the balance)

Number of subjects: 100

Statistical analysis: Pearson and Mann Whitney Correlation Test Chi-2 Test

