4. EVALUATION CRITERIA

4.1. MAIN EVALUATION CRITERION

FES-I questionnaire

This questionnaire comprises sixteen items. It is an improved version of the Fall Efficacy Scale (FES) proposed by Tinetti (18). The FES-I was developed by the Prevention of Falls Network Europe (ProFaNE). It is available on the ProFaNE website. A version of the FES-I scale has been translated into French. The questionnaire works as follows: for each proposition (16 in all), respondents are asked to rate their level of anxiety when imagining themselves carrying out the corresponding action. For each item, the respondent's level of concern is rated on a scale from 1 to 4, with the following correspondences:

- 1 not at all worried;
- 2 a little worried;
- 3 quite worried;
- 4 very worried.

The final score for this test is therefore between 16 and 64. The higher the score, the greater the fear of falling. The cut-point for this questionnaire, defining a high level of apprehension about falling, is set for scores greater than or equal to 28, according to research by (Delbaere et al, 2010)⁵

Hip goniometry

Hip goniometry: expressed in degrees, measures hip joint amplitude in active flexion and extension using a goniometer. The measurement is taken standing up. We evaluate one hip, the one that appears most mobile to the patient. With the goniometer at the level of the greater trochanter, we ask the patient to actively flex the hip, knee bent, checking that the lumbar vertebrae are not engaged. Same procedure on the same leg for straight-leg hip extension.

Modified Schober index

Modified Schober Index: This test is used to identify patients with ankylosing spondylitis (Macrae & Wright, 1969)⁶ and assesses lumbar joint mobility in flexion. Subsequent studies have shown the test to be reliable and reproducible (Koppenhaver *et al.*, 2011)⁷, (Malanga *et al.*, 2005)⁸.

- When the patient is standing, a first mark is made at the sacro-lumbar junction or between the posterior-superior iliac spines;
- a second mark is made 10 cm above the sacro-lumbar junction;
- a third mark is made 5 cm below the sacro-lumbar junction;
- a measuring tape is stretched between the three marks and the distance between the first and third marks is recorded, in neutral position and at maximum flexion of the lumbar spine;
- a deviation of less than 5 cm is considered pathological.

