12. QUALITY CONTROL AND ASSURANCE

12.1. DATA COLLECTION INSTRUCTIONS

All information required by the protocol must be recorded in the observation notebooks, and any missing data must be explained. Data should be collected as they are obtained, and transcribed neatly and legibly into the notebooks.

Erroneous data recorded in the observation notebooks should be clearly crossed out, and the new data should be copied next to the crossed-out information, accompanied by initials, date and, where appropriate, a justification by the person directing and supervising the research, or the authorized person who made the correction.

For the purposes of this study, data will be collected on a paper observation notebook.

Data collection will be carried out by: the investigator at each site

Data will be collected during the patient's stay and hospitalization.

The data collected in this study will be:

- Age
- gender
- History of falls
- Number of current drug treatments
- FES-I questionnaire score
- Hip goniometry in flexion
- Hip goniometry in extension
- Lumbar schober index

The data used in this study will come from: patients' medical records, the FES-I questionnaire and the measurements taken.

In order to carry out this study, pseudonymized data will be transmitted to the promotion unit of the clinical research unit

12.2. IDENTIFICATION OF DATA COLLECTED DIRECTLY IN THE CASE REPORT FORMS, WHICH WILL BE CONSIDERED AS SOURCE DATA

The observation book data used as source data are:

- FES-I score
- Schober index
- Hip goniometry in flexion
- Hip goniometry in extension

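### Section 8.8 stops a patient for any incomplete FES-I, even when the answered items already fix the primary group

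*Combined protocol and SAP*

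**What the plan says.** Section 8.8 gives "Incomplete FES-I questionnaire" as a stopping rule, beside inability or refusal to undergo a mobility measurement and the appearance of a non-inclusion criterion. It sets no minimum number of answered items, and no section gives a scoring rule for a partly completed questionnaire.

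Section 4.1 describes 16 items; for each, "the respondent's level of concern is rated on a scale from 1 to 4". It adds that "The final score for this test is therefore between 16 and 64", and the cut-point for high apprehension "is set for scores greater than or equal to 28". The Abstract gives the upper two categories as "20-27 moderately concerned, 28-64 very concerned by fear of falling". Section 9 merges the lower two categories into FES-I A, calls the top one FES-I B, and compares the three mobility measurements between A and B by Mann-Whitney tests. Its secondary analyses use the FES-I value itself (Spearman, regression) and the three categories.

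Section 12.1 lists "FES-I questionnaire score" among the data to collect; the 16 item responses are not listed. It also asks that missing data be explained.

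**The concern.** The primary analysis uses one binary fact about each patient's FES-I. In many partly completed questionnaires that fact is already settled, whatever the blank answer would have been. The rule nevertheless stops these patients, so it may cost the primary comparison outcomes that are known.

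Two things are at stake. The first is precision. The second is selection: the items ask patients to imagine carrying out actions, and the population is hospitalized or institutionalized. It is plausible, though the documents do not show it, that blanks are commoner in more dependent patients. Stopping them would then select on something related to both stiffness and fear. Replacing them would restore the numbers but not remove the selection.

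**Working it through.** **Inputs.** 16 items, each scored 1 to 4, cut-point 28 (section 4.1); A versus B as the primary contrast (section 9); 100 patients, 90% power, 5% risk (section 2.1.4). Not in the documents: the FES-I distribution, the rate of incomplete questionnaires, and the effect size, SD, group split and sidedness behind the sample size.

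**The plan's own figure.** Without those inputs, 100 patients cannot be reproduced, only back-solved. With a 50:50 split and two-sided 5%, d = (1.960 + 1.282) × √(1/50 + 1/50) = 3.242 × 0.2 = 0.648. This is used only for the power illustration below.

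**Bounds with m blanks.** If the 16 − m answered items sum to S, the total lies between S + m and S + 4m. The patient is certainly A if S + 4m ≤ 27 and certainly B if S + m ≥ 28.

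| Blanks | Certainly A | Certainly B | Open sums | Open / possible |
|---|---|---|---|---|
| 1 | S ≤ 23 | S ≥ 27 | 24-26 | 3 / 46 |
| 2 | S ≤ 19 | S ≥ 26 | 20-25 | 6 / 43 |
| 3 | S ≤ 15 | S ≥ 25 | 16-24 | 9 / 40 |
| 4 | never | S ≥ 24 | 12-23 | 12 / 37 |

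This step needs no assumption. With four blanks the lowest possible S is 12, and 12 + 16 = 28, so A can no longer be certain.

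For the three-category analysis with one blank, the cut at 20 adds S = 16-18 to the open sums, making 6 of 46.

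**Share of patients whose group is certain (assumed distributions).**

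- One blank, with truncated normal, scaled beta and shifted gamma totals: 82-94% for means 26-36 and SDs 8-12; 68-100% over means 22-45 and SDs 4-14.
- Three categories, one blank, same mid-range settings: about 66-90%.
- Item-level simulation (200,000 patients, item noise SD 0.7, nominal mean/SD 24/8, 30/10 and 36/12, blanks at random): 83%, 87% and 91% with one blank; 60-62%, 72% and 82% with two. Limiting items to 1-4 shifts the realised totals; nominal 24/8 becomes about 26/6.4.

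**Prorating the open one-blank cases.** Mean of answered items × 16, that is S × 16/15, gives 25.6, 26.7 and 27.7 for S = 24, 25 and 26. Rounded to whole numbers these are 26, 27 and 28, so 24 and 25 go to A and 26 goes to B. Without rounding all three would go to A, so the rounding must be written down. With rounding, in the same simulation:

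| Blanks | Which items are blank | Wrong group, all such patients |
|---|---|---|
| 1 | random | about 2-3% |
| 1 | highest-scored | 3-5% |
| 2 | highest-scored | 9-14% |

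Among open one-blank cases alone, about 17% are wrong with random blanks and about a third when the highest-scored item is blank. With two highest-scored items blank, 12-37% of true B patients are placed in A.

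**Power illustration.** Assume a 50:50 split, planned power of exactly 90% and no replacement; power = Φ(0.648 × √n / 2 − 1.960). If 10 of 100 patients are stopped, n = 90 gives 86.8%. Keeping 83-91% of those 10 gives n = 98.3-99.1 and 89.5-89.7%.

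**The case against.** The strongest case for the rule is that the plan does more with the FES-I than split it at 28. Spearman and regression need the score itself, and the three-category status is less often determined. Requiring a complete questionnaire gives one patient set for every analysis, which is defensible. This stands as far as the secondary analyses go, so a reader should not infer that the rule is needless throughout. It does not justify losing a primary outcome that is already known.

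Blanks may also be few. Section 6.1 selects patients able to understand and answer a questionnaire, and it is completed at a single visit. An action no longer performed can still be imagined and rated. This stands: the documents give no frequency, and even 10% stopped without replacement costs only about 3 points of power in the illustration.

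A reader might infer that the data are discarded for good. The documents do not say so. Section 8.8 is silent on whether a stopped patient's data are kept or the patient is replaced, and section 8.1 lets the study end once the required number is reached, which is compatible with replacement. Section 12.1 names the questionnaire as a data source and section 14.2 archives source files for 15 years, so item responses may survive. With one visit and no follow-up (section 8.2), exclusion is still the natural reading of being stopped.

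Finally, generous prorating would bring its own error if blanks fall on the most feared actions. This stands, and it limits the remedy.

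**Conclusion.** The concern holds in a limited form. The rule stops patients for any blank item, although one blank leaves the primary group open only for 15-item sums of 24, 25 or 26. That much follows from the documents alone.

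The share of one-blank patients whose group is certain, roughly 82-94% in mid-range scenarios and 68-100% over all those tried, rests on assumed score distributions. So does the 60-82% with two blanks. A single narrow percentage cannot be stated as fact, and the one-blank figure should not be applied to every incomplete questionnaire. The total loss is unknown because no rate of incompleteness is given. That the rule biases the association is a plausible risk, not something the documents demonstrate.

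**What to change.** Remove the incomplete questionnaire from the stopping rules in section 8.8, and add the 16 item scores to the notebook and to the list in section 12.1. Then prespecify in section 9:

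- **Primary comparison:** keep every patient whose A/B status the bounds decide, whatever the number of blanks. Where one blank leaves the group open, prorate (mean of answered items × 16, rounded to a whole number). Do not prorate for this comparison with two or more blanks; count the undecided patients and report them.
- **Spearman and regression:** use prorated totals, since these analyses need a score.
- **Reporting:** give the number of incomplete questionnaires and of blanks in each.
- **Sensitivity:** repeat the primary comparison with complete questionnaires only, and with prorated patients left out so that every group is certain. The second guards against prorating error, but it drops totals near 28, and with four or more blanks it can retain only B patients. The two should therefore be read together.

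The cost is an amendment to sections 8.8, 9 and 12.1 and a little more data entry. Assignment by bounds never misclassifies. Prorating would misplace about 17% of the open one-blank cases if blanks are random and about a third if the highest-scored item is blank, or about 2-5% of all one-blank patients, under the simulated distributions.

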10. RISKS AND VIGILANCE

This is a non-interventional study.

Adverse events observed in patients taking part in the research will be reported by the investigators in accordance with the systems put in place as part of healthcare vigilance.

11. ACCESS RIGHTS TO DATA AND SOURCE DOCUMENTS

11.1. ACCESS TO DATA

The Sponsor is responsible for obtaining the agreement of all parties involved in the research to ensure direct access to all research sites, source data, source documents and reports for quality control and audit purposes.

The persons directing and supervising the research will make the documents and individual data strictly necessary for monitoring, quality control and auditing of the research available to persons with access to these documents in accordance with the legislative and regulatory provisions in force.

11.2. SOURCE DATA

Any original document or object that can be used to prove the existence or accuracy of data or facts recorded in the course of research is defined as a source document.

For the purposes of this study, the source documents will be:

- Patient medical records
- Patient observation notebooks

11.3. DATA CONFIDENTIALITY

In accordance with current legislation, persons with direct access to source data will take all necessary precautions to ensure the confidentiality of information relating to the research, to the persons involved, and in particular to their identity, as well as to the results obtained. These persons, as well as the persons directing and supervising the research, are bound by professional secrecy.

During the research or at its conclusion, the data collected on the persons involved and transmitted to the promoter by the persons directing and supervising the research (or any other specialist) will be codified. Under no circumstances should the names or addresses of the persons concerned appear in plain text.

For coding purposes, only the first letters of the patient's surname and first name will be recorded, accompanied by a coded number specific to the research project, indicating the order of patient inclusion.

The promoter will ensure that each person taking part in the research has been informed of the access to individual data strictly necessary for the quality control of the research.

12. QUALITY CONTROL AND ASSURANCE

12.1. DATA COLLECTION INSTRUCTIONS

All information required by the protocol must be recorded in the observation notebooks, and any missing data must be explained. Data should be collected as they are obtained, and transcribed neatly and legibly into the notebooks.

Erroneous data recorded in the observation notebooks should be clearly crossed out, and the new data should be copied next to the crossed-out information, accompanied by initials, date and, where appropriate, a justification by the person directing and supervising the research, or the authorized person who made the correction.

For the purposes of this study, data will be collected on a paper observation notebook.

Data collection will be carried out by: the investigator at each site

Data will be collected during the patient's stay and hospitalization.

The data collected in this study will be:

- Age
- gender
- History of falls
- Number of current drug treatments
- FES-I questionnaire score
- Hip goniometry in flexion
- Hip goniometry in extension
- Lumbar schober index

The data used in this study will come from: patients' medical records, the FES-I questionnaire and the measurements taken.

In order to carry out this study, pseudonymized data will be transmitted to the promotion unit of the clinical research unit

12.2. IDENTIFICATION OF DATA COLLECTED DIRECTLY IN THE CASE REPORT FORMS, WHICH WILL BE CONSIDERED AS SOURCE DATA

The observation book data used as source data are:

- FES-I score
- Schober index
- Hip goniometry in flexion
- Hip goniometry in extension

12.3. DATA CIRCUIT

For each patient, data from the medical record and consultation (clinical examination and questionnaire) are collated in the observation notebook.

Data from the observation book is pseudonymized and entered into the database. The database is frozen and the data analyzed statistically.

The results of this study will first be presented in a thesis/internship report.

12.4. RESEARCH FOLLOW-UP

The clinical research unit at Melun Hospital will monitor the research. It will work with the research supervisor to check the content of the observation notebooks against the data entered in the database.

12.5. QUALITY CONTROL

Qualification of participants

The coordinating investigator, the qualified person or the person in charge of the research ensures that those involved in the research are qualified for the tasks they perform.

The persons responsible for quality control will take all necessary precautions to ensure the confidentiality of information relating to the research, to the persons involved, and in particular to their identity, as well as to the results obtained.

12.6. AUDIT AND INSPECTION

An audit may be carried out at any time by persons appointed by the sponsor, who are independent of those in charge of the research. Its purpose is to ensure the quality of the research, the validity of its results and compliance with the law and regulations in force.

The persons directing and supervising the research agree to comply with the requirements of the sponsor and the competent authority with regard to an audit or inspection of the research.

The audit may apply to all stages of the research, from protocol development to publication of results publication of results and the classification of data used or produced as part of the research.

12.7. DATA OWNERSHIP

The sponsor is the owner of the data and no use or transmission to a third party may be made to a third party without the sponsor's prior knowledge and consent.

13. **ETHICAL AND REGULATORY CONSIDERATIONS**

13.1. COMPLIANCE WITH REFERENCE TEXTS

The sponsor and the investigators undertake that this research will be carried out in compliance with the law, as well as in accordance with Good Clinical Practice and the latest version of the Declaration of Helsinki.

The research will be conducted in accordance with the present protocol. With the exception of emergency situations requiring the implementation of specific therapeutic acts, the persons directing and supervising the research undertake to comply with the protocol in all respects.

This research has received the favorable opinion of the Committee for the Protection of Persons (CPP) of *CPP's name on date*.

The sponsor will send the CPP's opinion and a summary to the National Agency for Medicines Safety (ANSM) for information.

The data recorded in the course of this research will be processed electronically within Southern Ile-de-France Hospital Group in compliance with the French Data Protection Act n°78-17 of January 6, 1978 and the European Regulation 2016/679 General Data Protection Regulation - RGPD.

This research is a RIPH3 using personal data under the responsibility of GHSIF. It is of public interest insofar as it contributes to research, studies, evaluation and innovation in the fields of health and medico-social care, and insofar as the information and collection of the non-objection of persons is prior to their inclusion.

Computerized processing of personal data will comply with the Reference Methodology for the processing of personal data in the context of health research in the health field" (MR-003).

The research promoter has signed a commitment to comply with this "Reference Methodology".

